**Background:**

Type 1 diabetes mellitus (T1DM) is one of the most common chronic diseases of childhood. In the US, it accounts for about two thirds of newly diagnosed diabetes in patients less than 19 years of age. It is caused by the autoimmune destruction of beta cells in the pancreas resulting in insulin deficiency. The Diabetes Control and Complications Trial demonstrated that improved glycemic control prevents and/or delays long-term complications associated with T1DM.

Improved outcomes in glycemic control have been seen in recent years with new insulin analogs and delivery devices. However, blood glucose control still remains imperfect and quality of life is affected by the continued dependence on insulin. Hence, the long term goal is to maintain beta cell mass in the pancreas. Higher residual beta cell mass early in the disease will result in long term benefits. To achieve this, various therapeutic trials have included therapies such as immunosuppression, immunomodulation, antigen specific therapy, islet cell transplant and stem cell transplant. However, these therapies have severe complications requiring further development. Therefore, until such therapies are available, other agents that have received FDA approval must be explored to improve glycemic control. Exenatide, a GLP-1 agonist, is one such agent that is approved for use in adults with type 2 diabetes mellitus (T2DM). Glucagon like peptide-1 (GLP-1) is secreted from the entero-endocrine cells following nutrient ingestion. It regulates glucose metabolism through its effects on the pancreatic islet cells, the gastrointestinal tract, and the central nervous system. The principal mechanisms include stimulation of insulin secretion, inhibition of glucagon secretion, delay in gastric emptying and reduction in food intake. In addition, GLP-1 has been shown to be important in beta cell proliferation and survival. In animal studies, GLP-1 is associated with induction of pancreatic duodenal homeobox 1 (pdx1) gene expression. Pdx1 is a transcription factor, which is primarily expressed in the endocrine pancreas and subsets of entero-endocrine cells in the duodenum. It is highly conserved among different species. Genetic disruptions of the pdx1 gene in mice abrogate normal pancreatic development and formation. In humans, inactivating mutations of the pdx1 gene is associated with pancreatic agenesis. Hence pdx1 is critical for pancreatic development and formation. GLP-1 actions may be mediated through pdx1 and thus influence beta cell proliferation and survival. Furthermore, GLP-1 regulates a subset of genes including pro-insulin, GLUT-2 and glucokinase that are known transcriptional targets of pdx1 action. GLP-1 has anti-apoptotic properties independent of its action on glucose regulation and islet proliferation. Apoptosis related cell

death is a feature of both type 1 and type 2 diabetes mellitus. In mice, with streptozotocin-induced diabetes, there is increased apoptotic related cell death. In these mice, treatment with exendin-4, a GLP-1 receptor analog, resulted in euglycemia significantly longer than those that were not treated with GLP-1. Conversely, mice with targeted disruption of the GLP-1 receptor gene exhibited increased apoptosis after streptozotocin administration. Furthermore, exendin-4 directly reduced cytokine-induced apoptosis in purified rat beta cells exposed to a host of cytokines such as interleukin 1a, tumor necrosis factor alpha, and interferon in vitro. Exenatide is a synthetic analog of exendin-4. It has properties similar to GLP-1 but has only fifty percent homology to native GLP-1. The investigator's brochure for exenatide suggests that in adults with T2DM, it was well tolerated at 0.1mcg/kg/dose and resulted in glucose lowering. GLP-1 is metabolized by di-peptidyl peptidases (DPP-IV) proteolysis and clearance occurs via the kidneys. However, in vitro studies with human placental DPP-IV demonstrated that exenatide is resistant to degradation by this enzyme. No evidence of plasma accumulation with multiple doses was noted in adults with renal dysfunction. Rodent models of hepatic disease with reduced liver function (thioacetamide-and D-galactosamine-induced liver injury) demonstrated no change in the pK role of the liver in the metabolism/ elimination of exenatide, suggesting that the liver does not play a major role in exenatide clearance. Adult studies demonstrate a dose-proportional Cmax and AUC in the 5-10 microgram dose range. The drug is rapidly absorbed with a Tmax of approximately 1-3 hours; mean Cmax values of 0.88-0.99 pmol/L (dose range 5-10 igm), and T $\frac{1}{2}$  beta of 2-4 hours. Bioavailability of exenatide was comparable whether injected subcutaneously in the arm, thigh, or abdomen. Exenatide has been extensively studied in patients with T2DM. Clinical studies indicate that exenatide is very effective in decreasing postprandial glucose excursions. Limited studies of GLP-1 infusions are reported in adults with T1DM. The principal mechanism of action is increased insulin release from the pancreatic islets, suppression of glucagon leading to decreased hepatic glucose production and decreased immediate postprandial hyperglycemia. In addition, exenatide delays gastric emptying and decreases food intake through centrally mediated mechanisms causing satiety and improved weight control. These effects result in the benefit of further reduction of Hemoglobin A1C (HgbA1C) beyond the reduction observed with insulin alone. Children and adolescents with new onset T1DM demonstrate marked increase in postprandial glucose concentrations despite the use of intense insulin therapy. Use of exenatide would be a novel way to reduce postprandial hyperglycemia and perhaps preserve beta

cell mass in the pancreas. Our hypothesis is that exenatide can reduce postprandial glycemic excursions by twenty percent compared to insulin mono-therapy in children and adolescents with new onset type 1 diabetes. In addition, we would like to study the safety of this low dose of Exenatide (1.25 micrograms) in new onset type 1 diabetes. The specific aims of this study are to determine the following: 1. The role of exenatide as compared to insulin mono-therapy in reducing postprandial hyperglycemia. 2. The role of exenatide on postprandial glucagon and gastric emptying. 3. The effect of long acting insulin/ **rapid acting insulin on a basal rate in an insulin pump** on postprandial glucose excursions, glucagon concentrations and gastric emptying. 4. Postprandial glucose excursions, glucagon concentrations and gastric emptying in normal healthy controls.

### **Study Design:**

A randomized, non-blinded trial with a crossover design will be used. Following informed consent and with appropriate subject assent, all subjects will have a screening visit. Following the screening visit, subjects with T1DM will undergo 3 studies: Part A (exenatide and long acting insulin), Part B (rapid and long acting insulin) and Part C (long acting insulin + rapid acting insulin + exenatide). **For Type 1 diabetes subjects who are on an insulin pump, for Part A they will be on their usual basal rate of rapid acting insulin and they would receive exenatide, for Part B they will be on their usual basal rate of rapid acting insulin and before they drink the boost milk shake, they will receive an insulin bolus according to their carbohydrate and sensitivity ratio's. For Part C they will be on their usual basal rate of rapid acting insulin and will also get exenatide and bolus of rapid acting insulin before they drink the boost milkshake.** The subjects will be admitted to the CRC on three separate occasions, at least 3-4 weeks apart. The three studies will be performed in a random order and the randomization will be done using a computerized system. The healthy controls will undergo a single study visit and will not receive any insulin or study drug. Except for the absence of diabetes, the healthy controls will be identical to the study subjects. Subjects with new onset diabetes will be compared to healthy controls. Inclusion Criteria: 1. Age between 12-18 years of age at the time of enrollment. 2. Diagnosed with antibody positive T1DM in the past 3 months. 3. Otherwise healthy except for their T1DM and treated hypothyroidism. 4. Females must have a negative pregnancy test. 5. Hemoglobin equal to or greater than 12 g/dl before each study. 6. Weight greater than 44 kg.

Exclusion Criteria: 1. Any chronic disease: leukemia, inflammatory bowel disease, cystic fibrosis, juvenile rheumatoid arthritis etc, except for diabetes and hypothyroidism. 2. Any medications that may affect glucose metabolism. 3. Abnormal AST, ALT, amylase, lipase, creatinine (more than 3 times normal values). 4. Lack of a supportive family environment as detected by the clinicians and/or social workers. 5. History of substance abuse (evaluated by medical history and CRAFFT questionnaire which will be administered at the screening visit). 6. Positive pregnancy test in females. 7. Lactating and nursing mothers. The study will include 10 subjects with T1DM and 10 healthy controls. The study is designed to detect a 20% difference in mean area under the curve for glucose for a 270 min period (breakfast). From our previous protocols, we have found  $r > 0.8$  between repeated measures and that the standard deviation for our excursion measure AUC is approximately 30%. With these specifications, the necessary sample size is 8 subjects. With a 20% drop out rate, we would need 10 subjects with T1DM. We will also recruit 10 healthy controls for comparison. Study Procedure: Screening: After signing a consent form, a screening evaluation will be performed prior to study enrollment. The evaluation will consist of a detailed medical history and physical examination (including height, weight, vital signs and Tanner staging). Baseline laboratory tests will include: CBC, creatinine, AST, ALT, amylase, and lipase. In addition, healthy control subjects will have a diabetes antibody panel drawn. A urine pregnancy test will be performed in all female subjects. The approximate volume of blood drawn is expected to be 3 ml's for subjects with T1DM and 11 ml's for controls. Study: The subject must be NPO (except for water) for 8 hours prior to the study. The subject will be admitted at 0700. Vital signs, stat hemoglobin (if there is no documented hemoglobin in the past 28 days), and pregnancy tests (in females) will be checked. Hemoglobin must be  $>12$  g/dl and female subjects must have a negative urine pregnancy test. An intravenous line will be placed in the forearm. At around 0800 baseline blood samples will be drawn for: glucose, insulin, C-peptide, amylin, GLP-1, and glucagon. In Study A and C, blood for exenatide will also be drawn. If blood glucose values are below 70 mg/dl, IV glucose of 5-15 grams will be administered to achieve euglycemia (90-130 mg/dl). At around 0830 (0 min), the subjects with T1DM will get his/her home dose of long acting insulin (if it has not been administered the night before). **Insulin Pump users will be on their usual basal rate of rapid acting insulin.** For study part A, **Exenatide will be also be given as a subcutaneous injection of 1.25 mcg.** For study part B, **bolus of rapid acting insulin will also be given based on subjects prescribed regimen.** For study

part C, the subject will receive Exenatide 1.25 micrograms and rapid acting insulin (with a 30-50% reduction from the usual dose). No medication will be given to subjects in the control arm. Following this, the subject will be offered a standard liquid meal of Boost High Protein Drink, 12 Oz. (360 calories, 50 g of carbohydrates and 12 g of fat) and asked to consume it within a 10-15 minute period. This will be enriched with 1 gram of [1- 13C] glucose. Blood glucose concentrations will be measured at the bedside using an Analox glucose analyzer at -30, -10, 0, 10, 20, 30, 40, 50, 60, 70, 80, 90, 100, 110, 120, 130, 140, 150, 160, 170, 180, 200, 220, 240, 270, 300 min. Blood samples will be collected for hormonal analysis of Insulin, C-peptide, Amylin at -30, -10, 0, 10, 20, 30, 40, 60, 80, 120, 180, 240, 300 min. Samples for GLP- 1 will be collected at -30, 0, 10, 20, 40, 60, 80, 120, 180, 240, 300 min and Glucagon at -30, -10, 0, 10, 20, 30, 40, 60, 80, 100, 120, 140, 180, 240, 300 min. Blood samples for pK exenatide will only be collected in Study A and C at -30, 0, 10, 20, 40, 60, 120, 180, 240, 300 min. A total blood volume of 148.7 ml's will be drawn in study A and study C, and 128.7 ml's in study B and the control study. Expired 13CO2 will be determined in breath samples at 0, 20, 40, 60, 120, 180, 240, 300 min. During the study, if blood glucose values in a subject are less than 55 mg/dl, IV glucose of 5-15 grams will be administered to achieve euglycemia (90-130 mg/dl). 1-2 doses of IV glucose should correct hypoglycemia. If more than 3 doses are required to achieve euglycemia, the study will be terminated, the subject will be offered a meal tray and blood sugar rechecked to ensure euglycemia. If blood sugar at any time is more than 350 with moderate ketones, the study will be terminated. At the end of the study at 300 min, lunch will be provided (consistent carbohydrate meal) and insulin will be given as per the subject's prescribed regimen. The subject will be discharged home with a designated driver due to the risk of hypoglycemia. A subject will be withdrawn from participating in the study if he/she meets any of the following conditions: 1) develops a chronic disease 2) develops anemia 3) becomes pregnant 4) develops a weight loss of greater than 10 pounds for unspecified reasons 5) loss of contact- if we are unable to reach a study subject (within 2 months of screening or completion of the first study) by phone or mail to schedule the next appointment. All study subjects (that are withdrawn from the study) will receive a phone call and a letter notifying them that they have been withdrawn. Blood samples will be kept for 20 years because some of the assays have not been developed for some of the hormone analyses. Since it is difficult to perform clinical studies in pediatrics, we feel it is

better to bank blood samples and perform hormone analyses as newer assays become available rather than repeating the study.

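### Do IV-glucose rescue and early termination inside the 270-minute window bias the planned glucose AUC comparison?

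*Protocol*

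**What the plan says.** All of this stands in the protocol.

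- **Measure** (Study Design, sample-size paragraph): "The study is designed to detect a 20% difference in mean area under the curve for glucose for a 270 min period (breakfast". The next sentence gives a within-subject correlation above 0.8 and says that "the standard deviation for our excursion measure AUC is approximately 30" percent.
- **Sample size** (same paragraph): "With these specifications, the necessary sample size is 8 subjects", then "With a 20% drop out rate, we would need 10 subjects with T1DM".
- **Hypothesis** (end of Background): "exenatide can reduce postprandial glycemic excursions by twenty percent compared to insulin mono-therapy".
- **Rescue** (Study Design, study procedure): if values during the visit "are less than 55 mg/dl, IV glucose of 5-15 grams will be administered to achieve euglycemia (90-130 mg/dl". One or two doses are expected to suffice; needing more than 3 ends the visit.
- **Termination on the high side** (same place): "If blood sugar at any time is more than 350 with moderate ketones, the study will be terminated".
- **Treatments**: Part A is exenatide without a rapid-acting bolus, Part B the prescribed bolus, Part C exenatide with a reduced bolus.

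Glucose is sampled from -30 to 300 min, and 270 min is one of the time points. Nothing says how a curve with rescue or early termination enters the AUC, or what baseline, if any, the AUC is taken above.

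**The concern.** The outcome is glucose over 270 min, and two rules act on that same glucose inside that window. Rescue lifts the lowest curves. Termination leaves some curves, including very high ones, without a full 270 min. The three parts give different mealtime insulin, so the events need not be equally frequent. Rescues could collect in Part B and high-side stops in Part A. Rescue glucose would then raise B and truncation would lower A, both in favour of exenatide. Randomised order does not remove an error that follows treatment, and with 8 evaluable subjects one or two events count.

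A second strand is the baseline. If the AUC is the whole area above zero while the hypothesis is about excursions, a 20% smaller excursion is a much smaller change in AUC, and the trial is powered for the wrong quantity.

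The natural remedy would be a baseline-subtracted AUC, with the last value before rescue or termination carried forward.

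**Working it through.** **1. The plan's own figure.** Inputs from the sample-size paragraph: SD 30%, r = 0.8, difference 20%. Two-sided 5% and 80% power are assumed, as the paragraph states neither.

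- SD of a paired difference = 30 × √(2 × (1 − 0.8)) = 18.97
- n = ((1.960 + 0.842) × 18.97 / 20)² = 7.06, rounded up to 8
- 8 / (1 − 0.20) = 10

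The stated 8 and 10 reproduce with the normal approximation. An exact paired t calculation on the same inputs gives 10 evaluable, a separate matter that does not bear on this point.

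**2. Size of one rescue.** From just under 55 to the 90-130 target is a rise of 35 to 75 mg/dl. Assume it lasts 60-120 min and that mean glucose is 150-200 mg/dl.

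- Smallest: 35 × 60 = 2,100; 2,100 / (200 × 270) = 3.9% of that visit's AUC
- Largest: 75 × 120 = 9,000; 9,000 / (150 × 270) = 22.2%

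These are shifts in one visit. The planned 20% is a difference in means, so the comparable figure is one eighth: 3.9 / 8 = 0.5 to 22.2 / 8 = 2.8 points. With wider assumptions (mean 120-200 mg/dl, duration 30-120 min), one rescue adds 1.9-27.8% to a visit. That is 0.2-3.5 points on the mean with one rescued subject and 0.5-6.9 with two.

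**3. Size of early termination.** Assume A and B both have mean 100, SD 30, r = 0.8, so the true difference is zero. Suppose the highest 10% or 20% of A curves stop at 150 min (assumed). The mean of the top fraction of a standard normal is 1.755 for 10% and 1.400 for 20%, so those curves average 152.7 and 142.0.

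| Handling | Top 10% | Top 20% |
|---|---|---|
| Summed raw to 150 min (120/270 = 44.4% lost, flat curve) | −0.10 × 0.444 × 152.7 = −6.8 | −0.20 × 0.444 × 142.0 = −12.6 |
| Pair dropped | −30 × 1.755 × (0.1/0.9) × (1 − 0.8) = −1.2 | −30 × 1.400 × (0.2/0.8) × (1 − 0.8) = −2.1 |

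A simulation with 8 subjects agrees: dropping the highest 1 or 2 A curves gives −1.2 or −2.3. The large figures therefore come from adding up curves of unequal length as if they were comparable. The protocol calls for no such step. It defines the measure over 270 min, and a curve stopped at 150 min does not supply it.

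**4. The baseline.** With an assumed pre-meal value of 120 and mean of 200 mg/dl, a 20% smaller excursion is 0.2 × (200 − 120) / 200 = 8% of total area. This matters only if the AUC is total area. The text specifies no baseline, and the sentence giving the SD names the quantity an excursion measure, as the hypothesis does. The pre-meal values at -30, -10 and 0 min are collected; nothing says they go unused.

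**5. The remedy.** On the same assumed values, an average excursion area is 80 × 270 = 21,600 mg·min/dl.

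- Rescue at 120 min (assumed), 54 mg/dl carried forward: (54 − 120) × 150 = −9,900. Post-rescue values of 90-130 would give −4,500 to +1,500. The visit falls by 5,400 to 11,400, or 25-53% of an average excursion, so hypoglycaemia is scored as benefit.
- Termination at 150 min, 350 carried forward: (350 − 120) × 120 = 27,600 from the imputed segment alone. That is 128% of an average excursion and contributes 128 / 8 = 16 points to an 8-subject mean.

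The imputation can move the result more than the rescue it is meant to correct.

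**The case for a change.** The strongest reply is that the conflict is in the text and not a matter of silence. The protocol fixes both the window and the rules that disturb it, and it expects hypoglycaemia to occur. None of its five withdrawal conditions covers a rescued or stopped visit, so such a subject stays in with an altered or incomplete curve. The 20% allowance is for dropout. The trial is not blinded, so the handling rule should exist before curves are seen.

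Much of this stands. The events can fall in the window, depend on the outcome and may differ between parts. The handling does affect the answer, and settling it before analysis is good practice. For A against B, rescues mainly in B and high stops mainly in A would both favour exenatide.

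It does not establish an error. The protocol nowhere says that rescued curves count as measured or that stopped ones are truncated or dropped. Even an AUC measured through rescue is a legitimate choice: it compares the regimens with their safety rules in force. The direction is not general either. Part C also contains exenatide, so rescue there works against it, and C against B is unclear. The high-side stop needs moderate ketones as well as the glucose value, and visits with more than 3 rescues stop on the low side too.

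On the baseline, calling the measure glucose AUC in one sentence and excursion AUC in the next is loose wording. It does not show that the area is taken from zero.

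**Conclusion.** The concern does not hold. It needs a rule for rescued and stopped curves that the protocol does not contain, and such a rule commonly belongs in the statistical analysis plan, which is not shown. Its second strand needs an AUC taken from zero, which the protocol does not state and its own label for the measure speaks against.

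The sizes do not rescue it. Against 20 points planned, one rescued subject shifts an 8-subject mean by 0.2 to 3.5 points over the widest range tried, and dropping the affected pairs costs about 1 to 2. Larger effects require several events in one part or raw summing of unequal curves. All of these rest on assumed glucose levels, durations, stop times and event shares; the protocol gives no event frequency, so neither the presence nor the size of a bias can be derived from it.

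Nor is the remedy a plain correction. Carrying values forward is a contestable choice. If the AUC were total area, moving to a baseline-subtracted one could undo the SD of 30% and the correlation above 0.8 on which the 8 subjects rest. No change to the protocol follows from this point.

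### Does leaving the glucose AUC undefined as total or above pre-meal level undermine the sample size of 8?

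*Protocol*

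**What the plan says.** Three statements bear on the scale of the measure.

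- Hypothesis (Protocol, Background): "exenatide can reduce postprandial glycemic excursions by twenty percent compared to insulin mono-therapy".
- Target for sizing (Protocol, Study Design, paragraph after the exclusion criteria): "The study is designed to detect a 20% difference in mean area under the curve for glucose for a 270 min period (breakfast").
- Variability (same paragraph): "the standard deviation for our excursion measure AUC is approximately 30" percent, with a correlation between repeated measures above 0.8, both taken from the team's previous protocols.

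The result is "With these specifications, the necessary sample size is 8 subjects", raised to 10 for 20% dropout. Alpha, power and the test are not written beside it.

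On the design: "A randomized, non-blinded trial with a crossover design will be used", and "The subjects will be admitted to the CRC on three separate occasions, at least 3-4 weeks apart", with the three studies in random order. On pre-meal glucose: "If blood glucose values are below 70 mg/dl, IV glucose of 5-15 grams will be administered to achieve euglycemia (90-130 mg/dl"). Glucose is read before the meal as well as after it: "Blood glucose concentrations will be measured at the bedside using an Analox glucose analyzer at -30, -10, 0, 10, 20" and onward to 300 min. Either form of AUC could therefore be computed from the planned samples.

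**The concern.** An excursion normally means a rise from a starting level, whereas an area under the glucose curve, without qualification, normally means the total area. A 20% cut in the rise is a smaller percentage of the total area. If the 20% belonged to one quantity and the 30% SD to the other, the 8 would rest on mismatched inputs.

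The design seems to sharpen this. Pre-meal glucose is corrected only when low, and a subject's visits are weeks apart, so starting levels can differ between visits. In a total AUC that difference passes into the within-subject contrast. With 8 to 10 subjects and no blinding, an open choice between two forms of the main measure could also be made after seeing data. At stake would be the adequacy of the sample size and the credibility of the main comparison.

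**Working it through.** **1. The protocol's own figure.** From the document: effect 20%, SD 30%, r = 0.8 (the lower limit of what is claimed). Assumed, because not stated: two-sided 5%, 80% power, one paired contrast.

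- SD of the difference = 30 × √(2 × (1 − 0.8)) = 18.97%
- n = (1.960 + 0.8416)² × 18.97² / 20² = 7.849 × 0.90 = 7.06, rounded up to 8
- With dropout: 8 / (1 − 0.20) = 10

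Both stated figures reproduce when the 20% and the 30% refer to one quantity.

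**2. Exact paired t-test, two-sided 5%.**

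| r | 8 completers | 10 completers |
|---|---|---|
| 0.80 | 72.5% | 84.2% |
| 0.85 | 83.8% | 92.7% |

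With 8, 80% power needs r of about 0.834. A one-sided 5% test at r = 0.8 gives 84.9% with 8. The protocol states r above 0.8 and promises no particular power, so 72.5% is the limiting case and contradicts nothing written.

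**3. What a mismatch of scales would do.** Let f be the share of total AUC lying above the pre-meal level. The protocol does not give f; 0.3 to 0.7 is assumed.

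- SD of 30% on total AUC, 20% on the excursion: the effect on total AUC is 20f, or 6% to 14%. Paired-t power with 8 is 12% to 44%.
- SD of 30% on the excursion, 20% on total AUC: the effect on the excursion is 20/f, or 67% to 29%. The normal approximation then needs only 1 to 4 subjects.

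The two mismatches point in opposite directions. The harmful one requires moving the 20% off the AUC, where the sizing sentence expressly puts it.

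**4. Pre-meal differences between visits.** A constant pre-meal level cancels from the within-subject difference and costs nothing. For differing levels, let w be the visit-to-visit pre-meal SD as a percentage of the mean excursion (assumed 5, 10 or 20; not in the protocol). Take the 30% and r = 0.8 to describe the incremental AUC. With ρ the correlation between pre-meal level and excursion:

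Variance of the total-AUC difference = 18.97² + 2w² + 2ρ × 18.97 × √2 × w

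| w | SD of difference, ρ = 0 | Power, 8 completers, ρ = 0 | Power, 8 completers, ρ = −0.5 |
|---|---|---|---|
| 5 | 20.25 | 67% | 83% |
| 10 | 23.66 | 54% | 81% |
| 20 | 34.06 | 30% | 50% |

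Incremental AUC stays at 72.5% throughout. Total AUC is worse when the two are unrelated. It is better at w = 5 or 10 when a higher start goes with a smaller rise. Total AUC with pre-meal glucose as covariate gives about 64% at ρ = 0 and 76% at ρ = −0.5 with 8. No form wins throughout.

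The losses at ρ = 0 also depend on the inputs being incremental while the analysis is total. If the earlier protocols' SD and r describe total AUC, visit-to-visit starting glucose is already inside them, and adding 2w² counts it twice.

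**5. Bias.** Visit order is randomised and every visit follows the same 8-hour fast and morning start. Remaining differences in starting glucose are chance with respect to treatment, so a comparison on total AUC is unbiased.

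**The case for a change.** The strongest case for the concern is that the sample size is fixed in the protocol, so its inputs should be defined there. The effect and the SD carry different labels in consecutive statements, and a reader cannot confirm the scale. In a small open-label crossover, a free choice of main measure is a recognised route to selective reporting, and naming the measure would cost only words.

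Part of this stands. The wording is loose, the AUC is not defined as total or incremental, and alpha, test and assumed r are absent beside the 8. But different labels are not different quantities: calling the AUC an excursion measure most naturally tells the reader that AUC is how the team measures excursion, which brings the hypothesis, the target and the SD together. The remaining items are ones a SAP commonly specifies, and a SAP may exist that is not shown here. The selection risk would be real only if nothing fixed the measure before analysis, and the protocol alone cannot show that. Nor is the preference for a baseline-corrected measure established, since it can lose power as well as gain it.

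**Conclusion.** The concern does not call for a change. No stated figure is wrong: 8 and 10 both follow from the protocol's inputs under the usual assumptions (two-sided 5%, 80% power, r = 0.8, normal approximation). The exact test is less generous at that lower limit of r, at about 73% with 8 and 84% with all 10, but the protocol claims a higher r and states no power target that it misses.

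The larger losses are conditional. The 12% to 44% range needs a reading that the sizing sentence does not support. The 67%, 54% and 30% need an assumed pre-meal SD, no link between starting level and rise, and inputs that do not already contain that variation. Randomised order removes the question of bias. What is left is a gap that an analyst fills by naming one AUC form, with alpha and test, before the data are examined.

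### Do 8 completers fall short of 80% power on the protocol's own inputs, and does having two exenatide parts make the shortfall worse?

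*Protocol*

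**What the plan says.** The Background section states one directional hypothesis: "Our hypothesis is that exenatide can reduce postprandial glycemic excursions by twenty percent compared to insulin mono-therapy". The Study Design section calls for a randomised, open crossover ("A randomized, non-blinded trial with a crossover design will be used") in which each subject with diabetes undergoes three studies: "Part A (exenatide and long acting insulin), Part B (rapid and long acting insulin) and Part C (long acting insulin + rapid acting insulin + exenatide". Parts A and C contain exenatide; Part B is insulin only.

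The sample size paragraph in the same section sets the target: "The study is designed to detect a 20% difference in mean area under the curve for glucose for a 270 min period (breakfast". It reports, from the investigators' previous protocols, a correlation between repeated measures of r > 0.8 and the spread: "the standard deviation for our excursion measure AUC is approximately 30" percent. From these it concludes "With these specifications, the necessary sample size is 8 subjects" and then allows for losses: "With a 20% drop out rate, we would need 10 subjects with T1DM".

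The paragraph gives no significance level, sidedness, target power or test, and does not say which pair of parts the 20% refers to.

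**The concern.** With 8 subjects the choice between a normal and a t calculation matters. The normal formula treats the SD as known, whereas a paired t-test on 8 subjects estimates it with 7 degrees of freedom. At r = 0.8 and two-sided 5%, that takes the power at n = 8 from 84.7% to 72.5%. Because the protocol allows for 20% dropout, 8 completers is its own planning case. If 80% was the aim, the trial would be described as designed to detect 20% when its 80%-power difference is 21.9%.

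The second strand is that both exenatide parts can be compared with Part B, while the calculation covers one comparison. If success in either comparison at an unadjusted 5% counted as confirming the hypothesis, the false-positive rate would exceed 5%. If alpha were split instead, power would fall further.

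**Working it through.** **Inputs from the protocol (sample size paragraph).** Difference 20%; SD 30%, read as the SD of a single AUC rather than of a difference; r > 0.8; dropout 20%.

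**Assumed, because not stated.** Alpha 5%, one- or two-sided; 80% as the benchmark for power; a paired comparison within subject.

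**Step 1: effect size at the bound r = 0.8.**
SD of the difference = 30 × √(2 × (1 − 0.8)) = 30 × √0.4 = 18.97%.
Standardised effect d = 20 / 18.97 = 1.054.

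**Step 2: reproduce the protocol's figure.**
Normal formula, two-sided 5%, 80% power: n = ((1.960 + 0.842) / 1.054)² = 7.06, rounded up to 8.
Dropout: 8 / (1 − 0.2) = 10.
Both stated figures reproduce.

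**Step 3: power with 8 completers under other readings** (noncentral t except in the first row).

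| Test at 5% | r | Power, n = 8 |
|---|---|---|
| Two-sided, normal approximation | 0.80 | 84.7% |
| One-sided paired t, 7 df | 0.80 | 84.9% |
| Two-sided paired t, 7 df | 0.80 | 72.5% |
| Two-sided paired t, 7 df | 0.82 | 76.9% |
| Two-sided paired t, 7 df | 0.83 | 79.1% |
| Two-sided paired t, 7 df | 0.834 | 80% |
| Two-sided paired t, 7 df | 0.85 | 83.8% |
| Two-sided paired t, 7 df | 0.90 | 94.9% |
| Two-sided t, error pooled over three periods, 12 to 14 df | 0.80 | 78.1% to 79.2% |
| Two-sided t, 6 df (one further df spent) | 0.80 | about 70% |

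The one-sided t-test at r = 0.8 has 79.2% power with 7 subjects and 84.9% with 8, so 8 is exactly the smallest number that reaches 80%. The hypothesis is worded as a reduction, so a one-sided reading is not far-fetched, although the protocol does not declare it.

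**Step 4: what the strict reading would require.** For the two-sided paired t-test at r = 0.8, power is 72.5% with 8, 79.1% with 9 and 84.2% with 10. It needs 10 completers, which is the number the protocol enrols. For r from 0.81 to 0.83 it needs 9, and from 0.84 it needs 8.

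**Step 5: two comparisons.** If A–B and C–B are each tested at 5% and either may confirm the hypothesis, simulation with n = 8 and equal correlations of 0.8 gives a family-wise error of 9.2%. With 2.5% for each, two-sided paired-t power at r = 0.8 is 58.0% with 8 completers and 73.1% with 10. These figures are correct for those procedures. The protocol describes neither procedure: it does not say that both contrasts will be tested at 5%, that either one suffices, or that alpha is to be shared.

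**The case for a change.** The best counter-argument is that a sample size cannot be called necessary without alpha, power, test and contrast, and that a later analysis plan cannot supply the basis for an enrolment figure already fixed in the protocol. On this view 0.8 is the only value of r supplied, so it is the natural planning value, and anyone who relies on a higher one should say so. The two-sided paired t-test is also a very common analysis for such a comparison, and under it 8 completers do fall below 80% at that value.

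Part of this stands. The documentation is thin: a reader cannot tell which calculation produced 8, and the single-contrast readings above run from about 70% to 85% at r = 0.8. If the normal formula was used, it was generous for so small a trial. The contrast behind the 20% is also not named.

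This does not establish the charge of a shortfall. A shortfall needs a stated standard, and the protocol sets none. The value r = 0.8 is the limit of the reported range, not a reported value, so for the two-sided 7-df test 72.5% is a floor rather than the protocol's power. Nor does 8 arise only from the large-sample formula, since two t-test readings also support it. The choice of primary contrast, its test and the order of testing are commonly set out in the statistical analysis plan, so their absence here is no finding.

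**Conclusion.** The concern does not hold. The stated 8 and 10 both reproduce, and no stated power or size is shown to be undelivered. The 72.5% is correct arithmetic for a two-sided 5% paired t-test with 7 df at r = 0.8, but the sidedness, alpha, test and 80% benchmark are all assumptions, and r is taken at a bound the protocol says is exceeded. With error pooled over the three periods the gap to 80% is 1 to 2 percentage points. With r of about 0.834 or more, or with a one-sided test, there is no gap. Even the strict two-sided reading asks for 10 completers, the number enrolled, and gives 84.2% if all complete.

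The multiplicity figures (9.2% family-wise error, 58.0% power with split alpha) depend on a decision rule that the protocol does not state. What remains is unstated detail about the calculation and the contrast, which alters neither enrolment nor any figure in the protocol. This conclusion assumes that the 30% is the SD of a single AUC, and it would need another look if an analysis plan fixed a two-sided test with an 80% target at r = 0.8 or let either contrast confirm the hypothesis without adjustment.
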